## **7.2 Disposition of Study Subjects**

Subject disposition and accountability of the study subjects will be summarized descriptively for all enrolled subjects. The definitions of subject disposition categories mentioned in section 19.4.2 of the study protocol will be used to categorize subjects.

## **7.3 Demographic and Baseline Characteristics**

Subject demographics, medical history, previously failed and actively taking AADs utilization and other baseline data will be summarized descriptively for all enrolled subjects. "Previously failed and actively taking AADs utilization" refers to the utilization of anti-arrhythmic drugs by the subjects prior to or at the time of enrollment, including any anti-arrhythmic drugs that the subjects may have taken in the past but did not work to control their arrhythmia and any anti-arrhythmic drugs that the participants are currently taking at baseline.

## **7.4 Endpoints and Associated Hypotheses**

### **7.4.1 Primary Safety Endpoint**

The primary safety endpoint is the occurrence of Primary Adverse Events (PAEs) within seven (7) days of the index ablation procedure where the investigational STSF catheter and TRUPULSE™ generator are used per the clinical investigation plan. The definition of PAEs can be found in section 7.3.1 of the study protocol.

To evaluate the primary safety objective of the study, the PAE rate will be compared against a performance goal (PG) of 12%. The formal hypotheses to test the primary safety endpoint is given as follows:

$$H_0: P_S \geq 0.12$$

and

$$H_A: P_S < 0.12$$

where  $P_S$  denotes the proportion of subjects with primary adverse events.

#### 7.4.2 Primary Effectiveness Endpoint

The primary effectiveness endpoint (PEE) is the acute procedural success, which is the achievement of the electrical isolation of targeted PVs at the end of the index procedure. The endpoint is confirmed by the confirmation of entrance block after adenosine/isoproterenol challenge, indicating that there is no electrical conduction from the left atrium into the targeted PVs.

To evaluate the primary effectiveness objective of the study, the acute effectiveness success rate will be compared against a PG of 90%. The formal hypotheses to test the primary effectiveness endpoint is given as follows:

$$H_0: P_E \leq 0.90 \quad \text{and} \quad H_A: P_E > 0.90$$

where  $P_E$  denotes the proportion of subjects with acute effectiveness success.

#### 7.4.3 Secondary Effectiveness Endpoint

The secondary effectiveness endpoint is freedom from documented (symptomatic and asymptomatic) atrial arrhythmia episodes including atrial fibrillation (AF), atrial tachycardia (AT), or atrial flutter (AFL) of unknown origin\* during the effectiveness evaluation period (Day 91-365). The AF/AT/AFL episodes will be identified based on electrocardiographic data.

Subjects with an AF/AT/AFL episode that is  $\geq 30$  seconds on arrhythmia monitoring device during the evaluation period device are considered failures of this long-term effectiveness endpoint. Acute procedural failure (i.e., failure to achieve entrance block with the study device in any of the targeted PVs) will also be deemed a failure of this endpoint.

To evaluate the secondary objective of the study, the 12-month effectiveness success rate will be compared against a PG of 50%. The formal hypotheses to test the secondary effectiveness endpoint is given as follows:

$$H_0: P_1 \leq 0.50 \quad \text{vs} \quad H_A: P_1 > 0.50$$

where  $P_1$  denotes the the proportion of subjects who are failure-free at 12-month follow-up.

\*AFL of unknown origin is defined as all AFL except those CTI dependent AFL as confirmed by 12-lead electrocardiogram (ECG) or entrainment maneuvers in an EP study.

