	
evaluation period (Day 91-Day 365). Acute procedure failure will also be considered failure of 12-month symptomatic recurrence free endpoint.
 
• Freedom from documented (symptomatic and asymptomatic) atrial arrhythmia (AF, AT or AFL of unknown origin*) episodes based on electrocardiographic data (≥ 30 seconds on arrhythmia monitoring device) during the effectiveness evaluation period (Day 91-Day 365) with extra failure modes. A subject who meets any of the following criteria will also be deemed an effectiveness failure:
- Failure to achieve acute procedural success.- Taking a new Antiarrhythmic Drug (AAD) (Class I / Class III) for atrial tachyarrhythmia (AF, AT or AFL of unknown origin*) or taking a previously failed Class I/III AAD at a greater than the highest ineffective historical dose for AF/AFL/AT during the effectiveness evaluation period (Day of 3-month visit – Day 365).- Greater than 1 repeat ablation for AF/AT or AFL of unknown origin in the blanking period or any repeat ablation for AF/AT or AFL of unknown origin* during the effectiveness evaluation period.• Use of a non-study device for the purpose of
- PVI (i.e., touch-up) among all clinically relevant targeted PVs and by subject- Ablation of left atrial non-PV AF targets (i.e., posterior wall) during index ablation procedure or for repeat procedures during blanking period.• Acute reconnection identified by adenosine/isoproterenol challenge among all clinically relevant targeted PVs and by subject• Repeat ablation procedures for left atrial arrhythmia (AF, AT or AFL of unknown origin*) within the 12-month FU period
- Percentage of subjects with repeat ablation during blanking period (≤ 90 days post index ablation procedure)- Percentage of subjects with repeat ablation after blanking period (Day 91 - 365 post index ablation procedure)- Percentage PV reconnection observed during repeat ablation procedures by targeted PVs treated at index ablation procedure and by subject- Percentage of subjects with repeat ablations due to non- PV targets• Quality of Life (QoL): the change of QoL assessed by comparing the Atrial Fibrillation Effect on Quality-of-Life (AFEQT™) scores before and at 3, 6 and 12- months after the ablation procedure.• Hospitalization for cardiovascular events through 12 months follow-up compared to 12 months prior to baseline. 
*AFL of unknown origin is defined as all AFL except those CTI dependent AFL as confirmed by 12-lead electrocardiogram (ECG) or entrainment maneuvers in an EP study.

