7.3.2 Secondary Hypothesized Endpoints

12-Month Effectiveness

Freedom from documented (symptomatic and asymptomatic) atrial arrhythmia (AF, AT or AFL of unknown origin*) episodes based on electrocardiographic data (≥ 30 seconds on arrhythmia monitoring device) during the effectiveness evaluation period (Day 91-Day 365) on or off antiarrhythmic therapy. Acute procedural failure (i.e., failure to achieve entrance block with the study device in any of the clinically relevant targeted PVs) will also be deemed a 12-month effectiveness failure.

**AFL of unknown origin is defined as all AFL except those CTI dependent AFL as confirmed by 12-lead electrocardiogram (ECG) or entrainment maneuvers in an EP study.*

Further refer to Appendix 2 for definitions on effectiveness terms.

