7.3.3 Additional Effectiveness Endpoints

PVI Durability Rate

- Percentage of targeted PVs in the index ablation procedure being durably isolated as confirmed by the electroanatomical mapping 75 days (+/- 15days) post index ablation procedure.
- Percentage of subjects with durably isolated targeted PVs as confirmed by the electroanatomical mapping at 75 days (+/- 15days) post index ablation procedure.

Single Procedural Success: defined as freedom from documented symptomatic atrial arrhythmia (AF, AT or AFL of unknown origin*) episodes based on electrocardiographic data (≥ 30 seconds on arrhythmia monitoring device) during the effectiveness evaluation period (Day 91-Day 365) following a single index ablation procedure.

Freedom from documented symptomatic atrial arrhythmia (AF, AT or AFL of unknown origin *) episodes based on electrocardiographic data (≥ 30 seconds on arrhythmia monitoring device) during the effectiveness evaluation period (Day 91-Day 365). Acute procedural failure will also be considered failure of 12-month symptomatic recurrence free endpoint.

Freedom from documented (symptomatic and asymptomatic) atrial arrhythmia (AF, AT or AFL of unknown origin*) episodes based on electrocardiographic data (≥ 30 seconds on arrhythmia monitoring device) during the effectiveness evaluation period (Day 91-Day 365) with extra failure modes. A subject who meets any of the following criteria will also be deemed an effectiveness failure:

- Failure to achieve acute procedural success.
- Taking a new Antiarrhythmic Drug (AAD) (Class I / Class III) for atrial tachyarrhythmia (AF, AT or AFL of unknown origin*) or taking a previously failed Class I/III AAD at a greater than the highest ineffective historical dose for AF/AFL/AT during the effectiveness evaluation period (Day of 3-month visit – Day 365).
- Greater than 1 repeat ablation for AF/AT or AFL of unknown origin* in the blanking period or any repeat ablation for AF/AT or AFL of unknown origin* during the effectiveness evaluation period.

Use of a non-study device for the purpose of:

- PVI (i.e., touch-up) among all clinically relevant targeted PVs and by subject
- Ablation of left atrial non-PV AF targets (i.e., posterior wall) during index ablation procedure or for repeat procedures during blanking period.

Acute reconnection identified by adenosine/isoproterenol challenge among all clinically relevant targeted PVs

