13.4 Repeat Ablation Procedures

Repeat procedures may be performed at the discretion of the investigator. It is highly recommended to collect arrhythmia documentation (in example documented recurrences) before performing a repeat procedure.

Repeat procedures **during the blanking period** (\leq 90 days post index ablation procedure) must be conducted with the investigational device, with or without focal touch-up, if the arrhythmia is due to PV triggers. If the arrhythmia is due to non-PV triggers and the subject is treated with a commercially available ablation catheter and generator, the subject will be excluded from the long- term effectiveness cohort. Procedures for CTI dependent flutter in the follow up period are not considered repeat procedures per CIP.

Repeat procedures performed **after the blanking period** (\geq 90- 365days post index ablation procedure) may be managed per investigator discretion using a commercially available ablation catheter and generator.

For the repeat procedures, the investigator must collect and provide information on location of reconnections of PVs and in case of atrial flutter recurrence, confirm if CTI dependent flutter or not. The follow-up schedule will remain based on the index ablation procedure.

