### 7.1.3 Handelling Subjects with Specific Ablation Scenarios in Effectiveness Endpoint Analysis

Subjects who undergo ablation using the investigational ablation system or commercial ablation devices at the **PV/CTI regions or outside the PV/CTI regions** will be included in the analysis of acute and long-term effectiveness endpoints according to the following guidelines:

- Condition 1: Subjects who undergo ablation **using the investigational ablation system for PV isolation** will be included in the analysis of acute effectiveness endpoints.
  - If the PV isolation is completed using commercial RF (radiofrequency) devices due to reasons related to the study system (SMARTTOUCH™ SF (STSF) and TRUPULSE™ Generator), the subject will be considered a failure for the acute effectiveness endpoint and be included in acute and long-term effectiveness endpoint analyses..
  - If the PV isolation is completed using commercial RF devices due to reasons unrelated to the study system (SMARTTOUCH™ SF (STSF) and TRUPULSE™ Generator), the subject will be considered not evaluable for the effectiveness of the investigational system and will be excluded from the analyses of acute and long-term effectiveness endpoints.
- Condition 2: The use of the **investigational ablation system outside the PV/CTI region is not permitted** according to the protocol. Subjects who undergo ablation outside the intended regions using investigational ablation system will be excluded from the long-term effectiveness endpoint analysis, unless they have already failed the acute effectiveness endpoint. Subjects who failed the acute effectiveness endpoint will also be considered failures for the long-term effectiveness endpoint.

- Condition 3: In cases where **commercial RF devices are used for ablation outside the PV region and/or CTI line** to treat arrhythmia identified during the procedure, it is allowed for the well-being of the patient. However, these subjects will be excluded from the long-term effectiveness analysis, as they received additional ablations beyond the intended treatment using non-investigational devices. This exclusion is necessary to avoid mixed effects from non-study devices that could confound the interpretation of the long-term effectiveness results for the investigational devices.

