## **7.10 Analyses of Secondary Effectiveness Endpoint**

If success is achieved in both the primary safety and acute effectiveness endpoints, then the secondary effectiveness endpoint will be evaluated using the exact test for a binomial proportion at a one-sided significance level of 2.5%. If the lower bound of the exact two-sided 95% confidence interval of the 12-Month effectiveness success rate is greater than the performance goal of 50%, the study will be considered to have demonstrated long-term (12-Month) effectiveness. Testing of the hypothesis for the secondary effectiveness endpoint ensures family-wise error rate is controlled at a 2.5% level after the success of the primary endpoints is met.

The secondary effectiveness endpoint will be performed in the PP analysis set when all subjects have completed their 12-month follow-up. The analyses results will be reported in the final CSR

The following additional analysis will be performed for the secondary effectiveness endpoint based on 12-month follow-up data:

- **Sensitivity to Analysis Set**

The secondary effectiveness endpoint will be analyzed in the mITT analysis set as a sensitivity analysis.

- **Kaplan-Meier Analysis**

Kaplan-Meier estimates and plots will be used to characterize the time to first failure event of the secondary effectiveness endpoint, including acute effectiveness failure, recurrence of documented symptomatic/asymptomatic AF/AT/AFL episodes during evaluation period. The probability of freedom from the secondary effectiveness endpoint failure at each follow-up timepoint post blanking will be presented. The KM analysis will be performed in the PP and mITT analysis sets.

- **Best-case Scenario**

The point estimate for freedom from secondary effectiveness failure will be estimated by treating subjects with missing secondary effectiveness outcomes as free from secondary effectiveness events.

- **Worst-case Scenario**

The point estimate for freedom from secondary effectiveness failure will be estimated by treating subjects with missing secondary effectiveness outcomes as failures.

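### A repeat ablation after Day 90 is not a failure of the tested 12-month endpoint, so a re-ablated subject with no qualifying tracing on Day 91-365 counts as a success of the study system

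*SAP*

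**What the plan says.** Protocol 7.3.2 and 19.4.5 and SAP 7.4.3 define the secondary endpoint, which is tested against 50% only after both primary endpoints are met. The first failure route is a documented episode of AF, AT or AFL of unknown origin lasting at least 30 seconds "during the effectiveness evaluation period (Day 91-Day 365) on or off antiarrhythmic therapy". The second is acute procedural failure: not achieving entrance block with the study device "in any of the targeted PVs) will also be deemed a failure of this endpoint". The Kaplan-Meier analysis in SAP 7.10 uses the same two events, "including acute effectiveness failure, recurrence of documented symptomatic/asymptomatic AF/AT/AFL episodes during evaluation period".

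On repeat procedures after blanking, protocol 13.4 says that they "may be managed per investigator discretion using a commercially available ablation catheter and generator". On evidence beforehand it says: "It is highly recommended to collect arrhythmia documentation (in example documented recurrences) before performing a repeat procedure".

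Repeat ablation does count as failure elsewhere. The additional endpoint with extra failure modes (protocol 7.3.3, SAP 7.4.4.3) includes "any repeat ablation for AF/AT or AFL of unknown origin* during the effectiveness evaluation period", and SAP 7.4.4.3 makes a repeat procedure for the study arrhythmia a failure of Single Procedural Success. SAP 7.11.3 also reports the percentage re-ablated after blanking and the time to first repeat. SAP 7.4.4 states that no additional endpoint is formally tested.

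**The concern.** The 12-month claim is made for the study system. A second ablation inside the evaluation window suggests that the first treatment was not enough, and it may prevent the recurrences that the endpoint looks for. If no qualifying tracing was captured on Day 91-365, the tested endpoint records neither fact and scores the subject as a success, even when the later rhythm control came from another system.

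The plan recognises this kind of confounding at the index procedure. SAP 7.1.3 Condition 3 excludes subjects given commercial ablation outside the PV region or CTI line and explains: "This exclusion is necessary to avoid mixed effects from non-study devices that could confound the interpretation of the long-term effectiveness results". No corresponding rule covers a commercial re-ablation of the pulmonary veins after Day 90. Compared with counting these repeats as failures, the present definition can only give the same or a higher success rate.

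**Working it through.** **1. Following a subject through the rules.** Take a subject with acute success who is re-ablated after Day 90 with a commercial system and has no recorded episode of 30 seconds or more on Day 91-365. Two routes lead there:
- The recurrence was documented only in blanking, which protocol Appendix 2 does not count as failure.
- There were symptoms after Day 90 but no strip was captured.

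The rules that could apply are:
- SAP 7.4.3: neither failure route is met.
- SAP 7.8.3: with at least 335 days of follow-up and monitoring, the outcome is not missing.
- Protocol 13.4 and the last bullet of SAP 7.1.3: the exclusions for other systems used at a repeat apply during blanking only.
- SAP 7.1.3 Conditions 1 to 3 and the per-protocol definition in protocol 19.3: these concern the index procedure or ablation outside the PV/CTI regions.
- SAP 7.1.4: an ablation for AF, AT or AFL after 90 days is a repeat failure, but only at a durability re-map visit and under an endpoint that includes repeat-procedure failure, which SAP 7.4.3 does not adopt. The re-map window ends at Day 75 + 15 = 90, so this rule reaches only late re-map visits.
- SAP 7.10: the best-case and worst-case analyses reassign missing outcomes only, and the mITT analysis keeps the same definition.

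The subject is an evaluable success in the test and in every planned sensitivity analysis of it.

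**2. Reproducing the plan's power.** Inputs from SAP section 6 and 7.10: p0 = 0.50, p1 = 0.65, exact binomial test, one-sided 0.025, N = 100 with 10% missing. The critical count r is the smallest r with P(X ≥ r | n, 0.50) ≤ 0.025. Power is P(X ≥ r | n, 0.65).
- n = 100 × 0.90 = 90: r = 55, attained alpha 0.0223, power 81.2%.
- n = 100: r = 61, attained alpha 0.0176, power 82.8%.

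The stated power above 80% is reproduced, so the sample-size arithmetic is sound. Applying the same 10% to the full enrolment gives 135 × 0.90 = 121.5, taken as 121: r = 72 (59.5%), attained alpha 0.0225, power 91.2%.

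**3. Effect on the test.** Let d be the share of analysed subjects who are re-ablated after Day 90, have no qualifying tracing and so count as successes. The documents give no value for d; 1 to 5 points is an assumed range (about 1 to 6 subjects of 121, or 1 to 4 or 5 of 90).
- Chance of passing when the rate with these subjects as failures is 50%: P(X ≥ r | n, 0.50 + d).
- Power if they are counted as failures and the rate under the current definition is 65%: P(X ≥ r | n, 0.65 − d).

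| d (assumed) | Pass, n = 90 | Pass, n = 121 | Power, n = 90 | Power, n = 121 |
|---|---|---|---|---|
| 0 | 2.2% | 2.3% | 81.2% | 91.2% |
| 1 point | 3.5% | 3.7% | 75.4% | 86.9% |
| 2 points | 5.2% | 5.9% | 68.7% | 81.4% |
| 3 points | 7.5% | 8.9% | 61.4% | 74.6% |
| 5 points | 14.5% | 18.3% | 46.0% | 58.3% |

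**4. Margin in subjects.** At 65%, 0.65 × 90 = 58.5. With 58 successes and 55 needed, moving 4 subjects to failure reverses the result. For 121, 0.65 × 121 = 78.65. With 78 successes and 72 needed, 7 subjects reverse it.

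**The case against.** The endpoint is a rhythm outcome that accepts antiarrhythmic drugs, so tolerating further rhythm treatment may be deliberate. The stricter composite, Single Procedural Success and the repeat-ablation summaries are all pre-specified, so a reader of the report will see the crossover. That stands as to disclosure. None of those outputs shows what happens to the tested rate or to the decision against 50%.

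The gap is also narrow. Subjects hold a remote monitor and are asked to transmit when they have symptoms, and unscheduled visits can include ECG and Holter. Any qualifying episode on Day 91-365 already makes the subject a failure. A reader might infer that every post-Day-90 re-ablation is scored as a success; the documents do not support that. The clearest leak is a recurrence documented only in blanking and treated after Day 90.

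Three further limits stand. Condition 3 of SAP 7.1.3 concerns non-PV/CTI ablation at the index procedure, and its remedy is exclusion; it shows that the sponsor recognises the confounding but does not itself require failure coding here. Protocol 5.3 takes the 50% goal from a consensus statement, and the documents do not say whether that benchmark counts repeats as failures. Finally, counting repeats as failures is not free: if such subjects are common, the power loss is substantial.

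**Conclusion.** The gap is real on the text. A subject re-ablated after Day 90 without a qualifying tracing on Day 91-365 is a success of the tested endpoint, the bias can only favour the device, and no planned sensitivity analysis of the gated test addresses it.

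The size is conditional. If the rate with these subjects counted as failures were exactly 50%, an assumed lift of 1 to 5 points takes the chance of passing above the nominal 2.5% throughout the range in the table. The lift counts only subjects who also stay free of recorded episodes to Day 365, because a later qualifying recurrence makes them failures anyway.

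Two stronger readings are not supported. One is that the 12-month result will be inflated by a known amount: the documents give neither a post-blanking repeat rate nor the share without a tracing. The other is that study success is at risk: SAP 7.5.3 rests that on the two primary endpoints at 3 months, so only the 12-month claim is affected. Nor is this a comment on which system should be used for a repeat; it concerns scoring only.

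**What to change.** In protocol 7.3.2 and 19.4.5 and SAP 7.4.3 and 7.8.3, state that any repeat ablation for AF, AT or AFL of unknown origin on Day 91-365, with any device, is a failure of the secondary endpoint on the date of the procedure. Use the same event in the Kaplan-Meier analysis of SAP 7.10. Keep two exemptions: procedures for CTI-dependent flutter, as in protocol 13.4, and durability-subset re-map ablations without proven AF, AT or AFL, as in SAP 7.1.4.

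If the sponsor keeps the current definition, add to SAP 7.10 a sensitivity analysis that repeats the exact test against 50% with these subjects counted as failures, and report it beside the gated result.

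Either change takes a few sentences and no new data, since repeat ablations are already recorded at follow-up visits. Redefinition also costs a less favourable success rate and some power, more so as such subjects become more common: with 121 analysed and an assumed 65%, power falls from 91% to 87% at 1 point and to 58% at 5 points. The sensitivity analysis leaves the power of the gated test unchanged.
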